7.3. Trial completion and post-trial therapy

The trial for a patient will be considered completed after the 6th visit on the 30th day after thrombolysis.

Therapy after the study will be carried out in accordance with current guidelines.

7.4. Criteria for early termination of trial participants

A patient should be withdrawn from the trial immediately after any of the following situations occur:

- a patient or his/her legal representative or attending physician sends a request to exclude the patient from the trial, based on the withdrawal of Informed consent form (the patient's unwillingness to continue participation in the trial);
- pregnancy;
- significant violation of the Protocol procedures;

The reason for each unscheduled termination should be noted in the case report form (CRF) in the section «Trial Completion». Follow-up will be performed for all patients who have dropped out of the trial due to adverse events or other safety parameters.

Follow-up will also be performed for all patients who have dropped out of the trial for other reasons, but also experience adverse events or have other safety parameters that might lead to discontinuation of therapy. In the case of early termination, the treatment of the underlying disease continues in accordance with guidelines and health standards.

Follow-up should be continued until the patient's condition is restored; until the diagnosis of an adverse event or a change in the safety parameter is stabilized or established chronically; as long as there are clinical indications for follow-up, or the duration of follow-up is determined by an attending physician-investigator.

In the case of pregnancy, every effort should be made to fully monitor the course of pregnancy until the moment of delivery, and child growth.

Randomized patients who did not complete the trial for reasons including those related to the trial drug will be included in the analysis of efficacy and safety data. Replacement of the removed randomized patients with newly included ones is not allowed.

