Official Title:	Multicenter open-label randomized comparative trial of the efficacy and safety of single bolus injection of Fortelyzin® («SuperGene», LLC) and bolus-infusion of Actilyse® (Boehringer Ingelheim Pharma GmbH) in patients with massive pulmonary embolism (PE)
Short title:	FORPE
Trial phase:	III b
Trial aim:	Assessment of the efficacy and safety of single-bolus intravenous injection of Fortelyzin® in comparison with bolus infusion of Actilyse® in patients with massive PE
Trial objectives:	
• To assess the efficacy of single-bolus intravenous injection of Fortelyzin® in comparison with bolus infusion of Actilyse® in patients with massive PE• To assess the safety and possible adverse events of single-bolus intravenous injection of Fortelyzin® in comparison with bolus-infusion of Actilyse® in patients with massive PE
Trial design:	A multicenter, open-label, randomized, comparative, parallel-group non-inferiority trial of efficacy and safety. In clinical centers, patients will be randomized using the «envelope method» into two equal groups of 155 patients each (a total of 310 people, including 10 % of those who may have dropped out) and assigned to receive either Fortelyzin® or Actilyse®. The drugs will be administered after signing the informed consent. Fortelyzin® in a dose of 15 mg

	
will be given as single i.v. bolus over 10-15 seconds. Actilyse® will be administered in accordance with the instruction for use. Patients will be monitored for 30 days: 1-2 days in the Intensive Care Unit and the Department of cardiology in the remaining days before discharge (on average 14 days), with an outpatient visit on the 30th day.
 
Enrollment of patients into the trial will be conducted on a competitive basis.

Trial duration:	The trial completion date is the 30th day after the final trial patient was included in the trial. All patients will be examined for 30 days
Trial population:	Men and women aged 18 years and older with a diagnosis of massive PE
Sample size:	The total number of patients included in the trial – 310 people, including 10 % of possible dropouts

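### Section 7.4 ends trial follow-up for randomized patients after an undefined protocol violation, so mortality status, mainly at day 30, can be missing for patients the plan means to analyse

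*Combined protocol and SAP*

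**What the plan says.** Section 7.4 states: "A patient should be withdrawn from the trial immediately after any of the following situations occur". It lists three situations: a request based on withdrawal of consent, pregnancy, and "significant violation of the Protocol procedures". The withdrawal is from the trial, not only from study treatment. No section defines the third situation or says who judges it.

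Follow-up after withdrawal is conditional. Patients who leave because of adverse events or safety parameters are followed. For the rest the text reads: "Follow-up will also be performed for all patients who have dropped out of the trial for other reasons, but also experience adverse events" (comparable safety parameters also count). Pregnancy is followed separately. Follow-up lasts until recovery or stabilization, for as long as it is clinically indicated, or "the duration of follow-up is determined by an attending physician-investigator".

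The same section also says "Randomized patients who did not complete the trial for reasons including those related to the trial drug will be included in the analysis", and this covers efficacy as well as safety. It then rules out substitution: "Replacement of the removed randomized patients with newly included ones is not allowed".

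On general follow-up, the protocol summary says "All patients will be examined for 30 days" and section 7.3 says "The trial for a patient will be considered completed after the 6th visit on the 30th day after thrombolysis". Section 11 makes all-cause death by day 7 the primary endpoint. All-cause death by day 30 is a secondary endpoint and part of the composite. Section 18 defines no analysis set and gives no rule for a patient whose vital status is unknown.

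**The concern.** The plan commits to analysing patients whose outcome nobody is required to collect. A patient withdrawn for a violation while free of adverse events has no further scheduled contact. A later death would meet the serious adverse event definition in section 12, but nothing in the schedule would bring it to light. Day 30 is the main exposure, because it depends on an outpatient visit that a withdrawn patient no longer has.

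The trial is open-label and the trigger is discretionary, so violations may be judged with the arm known. Losses that arise this way cannot be assumed unrelated to arm. In a non-inferiority trial with mortality as the endpoint, unseen deaths concentrated in the Fortelyzin arm would push the result towards a non-inferiority conclusion.

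**Working it through.** **Inputs from the protocol.** Section 17: expected mortality 10% in both arms, margin 10 points, one-sided 2.5%, 80% power, 141 per arm raised to 155 for 10% dropout. Section 8: hospital stay averaging 14 days, then an outpatient visit on day 30.

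**Assumptions.** The number lost, L per arm, is not given, and the dropout allowance is not split by reason. I vary L up to 15, which is about 10% of 155. Section 18 names no interval for the risk difference, so I use the Newcombe 95% interval and give the Wald interval where it matters.

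**1. The plan's own figure.** n = (1.960 + 0.842)² × [0.1×0.9 + 0.1×0.9] / 0.10² = 7.849 × 0.18 / 0.01 = 141.3, which agrees with 141. Then 141 × 1.1 = 155.1, giving 155 per arm and 310 in total.

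**2. Does another section close the gap?**
- The summary and section 7.3 describe ordinary completion. Neither says that withdrawn patients continue.
- Section 12 has patients monitored until an adverse event resolves. This does not reach a patient without one.
- Section 19 has the monitor check compliance but does not say who decides that a violation is significant.
- Section 18 is silent on unknown status.

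**3. Day 30 (no margin is set).** With equal known deaths, the all-randomized difference can lie anywhere within ±L/155 of zero: 1/155 = 0.6 points, 5/155 = 3.2 points, 15/155 = 9.7 points.

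**4. Day 7, extreme split.** Start from equal observed deaths, then count every lost Fortelyzin patient as dead and every lost Actilyse patient as alive. The Newcombe upper limit is (p₁ − p₂) + √[(u₁ − p₁)² + (p₂ − l₂)²], where u₁ and l₂ are Wilson limits. For 20/155 v 15/155 it is 0.0323 + √[(0.1909 − 0.1290)² + (0.0968 − 0.0595)²] = 0.1045.

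| Observed deaths per arm | Lost per arm | After extreme split | Upper limit (points) |
|---|---|---|---|
| 15 | 4 | 19/155 v 15/155 | 9.72 |
| 16 | 4 | 20/155 v 16/155 | 9.88 |
| 15 | 5 | 20/155 v 15/155 | 10.45 |
| 17 | 4 | 21/155 v 17/155 | 10.03 (Wald 9.88) |

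On observed cases alone, these even results have upper limits of 6.95 to 7.30 points. The smallest loss per arm that overturns an even result is 7 at 8 observed deaths, 6 at 9–12, 5 at 13–16, 4 at 17–22 and 3 at 23.

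**5. Day 7, chance of overturning.** Deaths among the lost are taken as binomial, with 10% mortality in lost Actilyse patients.

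| Lost per arm | Observed deaths per arm | Lost Fortelyzin mortality 10% | 20% | 30% |
|---|---|---|---|---|
| 5 | 15 | 0.001% | 0.02% | 0.14% |
| 5 | 17 | 0.03% | 0.41% | 1.9% |
| 8 | 15 | 0.02% | 0.51% | 3.1% |
| 15 | 14 | 0.35% | 6.2% | 24.9% |

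**6. Type I error under arm-related loss.** Suppose true mortality is on the margin (20% v 10%) and only observed cases are analysed. If lost Fortelyzin patients die at 30% to 50%, the one-sided error rises from 2.5% to 3.4%–5.8% with 5% lost, and to 4.5%–12.8% with 10% lost.

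**7. Power if loss is unrelated to outcome.** Φ(0.10/√(0.18/n) − 1.96) gives 83.5% at 155 per arm, 82.3% at 150 and 79.6% at 140. The issue is bias and not power.

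**The case against.** The case for calling this minor has weight.

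- **Day 7 is largely covered.** The stay averages 14 days and treatment of the underlying disease continues after termination, so day-7 status is normally in hospital records. This stands and limits the primary risk.
- **The exposed group is a fraction of the dropouts.** The 10% allowance covers every reason for leaving. Consent withdrawal can legitimately end data collection. Adverse events are defined so broadly (any adverse symptom or laboratory deviation) that few patients in shock will be free of them. This stands too. The allowance is also strictly 155 − 141 = 14 per arm, against the 15 used above.
- **The larger figures rest on assumptions.** The 24.9% needs the whole allowance lost by day 7 and tripled mortality among the lost in one arm only. The interval matters as well: at 5 lost and 17 observed deaths, the 1.9% falls to 0.22% with Wald limits. Open-label design and an unnamed judge make arm-related loss possible; they do not show that it is likely.
- **Day-30 death is secondary, with no margin.** The L/155 bound would apply to missing outcomes in any trial.
- **An analysis of known status sits awkwardly with section 7.4**, which includes non-completers. Collecting status for nearly everyone brings the two close together, and the sensitivity analysis covers the remainder.

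None of these points supplies a day-30 status for a withdrawn patient without adverse events.

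**Conclusion.** The concern holds. As written, section 7.4 can leave mortality unknown for patients the plan intends to analyse, mainly at day 30. The primary conclusion is at small risk. With 8 to 16 observed deaths per arm, 4 lost per arm cannot overturn an even result. With 5 lost and 15 observed deaths, it takes the extreme split. In the scenarios with equal 10% mortality among the lost, the chance is at most 0.35%. It becomes material only when losses are both sizeable and arm-related, as in the 15-lost scenario. These figures rest on assumed loss numbers, assumed mortality among the lost and an assumed interval method. The text gap rests on none of them. This should be corrected because the remedy is cheap and status not collected on time may be hard to recover. It does not by itself undermine the trial.

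**What to change.** **Section 7.4.** Record significant protocol violations as deviations and not as a reason to end trial follow-up. Add: *Vital status at day 7 and day 30 is collected from hospital records or by telephone for every randomized patient, regardless of withdrawal or deviation, unless consent to data collection is itself withdrawn.*

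**Section 18.** Add: *Every randomized patient stays in the assigned arm. The primary analysis of day-7 death uses all patients with known status. Patients with unknown status are reported by arm and reason. A tipping-point analysis varies their status up to the extreme of all unknown Fortelyzin patients dead and all unknown Actilyse patients alive. The same rule applies to day-30 death.*

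What may be collected after consent is withdrawn depends on the consent text, which is not in this copy, and should be checked against it.

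**Cost.** Protocol wording, a day-7 and a day-30 status entry for each withdrawn patient (at most 31 patients if the full 10% of 310 withdrew), some by telephone, and one short sensitivity analysis. The change affects data collection and analysis only. Treatment and sample size stay as they are.

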7.5. Criteria for early termination of the trial

The trial may be completed prematurely:

- if the trial reveals serious adverse events associated with the use of the trial drug and makes its further use unacceptable from an ethical point of view;
- when new information is received that indicates a high risk for the trial participants;
- in the case of circumstances considered as force majeure events;
- at the request of the Federal Regulatory Authorities and at the decision of the Sponsor.

7.6. Exclusion of clinical site

The trial conducted at a separate clinical site may be terminated if the Sponsor, Investigator, Regulatory Authorities, or the Ethics Committee of the clinical site deem it necessary for any reason.

8. DESIGN AND PLAN OF RESEARCH ACTIVITIES

This trial is a multicenter, open-label, randomized, parallel-group, phase III b non-inferiority trial to compare the efficacy and safety of the trial drug.

The trial will include 310 patients with massive PE. The patients will be monitored for 30 days: 1-2 days in the Intensive Care Unit and the Department of cardiology in the remaining days before discharge (on average 14 days), with an outpatient visit on the 30th day.

Start of research, initiation of centers: «_____» 20____

Enrollment of patients: «_____» 20____

Result processing and reporting: «_____» 20____

The enrollment period may be extended to total patient enrollment if a research center fails to enroll the planned number of patients. The end date of the trial is considered to be the end date of the trial in all patients involved.

In each research center, the subject of the trial is assigned a serial number that corresponds to the sequence of patient inclusion in the trial. The serial number is reflected in the CRF. The list of patient's identification is stored in the trial file. Patients are included in the trial only after signing the Informed consent form.

Before the trial, all patients will undergo the following procedures: collection of thorough medical history, signs of hemodynamic collapse, risk stratification to assess the prognosis according to the PESI classification, a physical examination, CTPA, ECG, EchoCG with the definition of PASP, ultrasound diagnostics of the inferior vena cava will be performed; blood and urine samples will be taken for laboratory tests:

- **complete blood count:** hemoglobin, red blood cells, hematocrit, leukocyte formula: neutrophils, eosinophils, basophils, monocytes, lymphocytes, platelets, ESR;
- **biochemical blood parameters:** total protein, creatinine, urea, AST, ALT, CK, NT-proBNP, total bilirubin, glucose, sodium, potassium, total cholesterol, HDL-cholesterol, triglycerides;

- **coagulogram:** fibrinogen, aPTT, INR, prothrombin, D-dimer.
- **general urine analysis:** red blood cells.

After enrollment, patients will be randomized using the «envelope method» into two equal groups of 155 patients each (a total of 310 people, including 10% who may have dropped out) and assigned to receive either Fortelyzin® or Actilyse®. Fortelyzin® will be given as single i.v. bolus over 10-15 seconds. Actilyse® will be administered following the instruction for use.

To compare the efficacy and safety of Fortelyzin® vs Actilyse®, patients will be monitored for 3 days after administration of the drug. During this period, patients will have 6 visits (Table 5).

Table 5. FORPE trial plan

Procedure	Visit number and its period	V ₁	V ₂	V ₃	V ₄	V ₅	V ₆
		0	Day 1	Day 2	Day 7	At discharge	Day 30 (outpatient)
Inclusion and exclusion criteria		+	–	–	–	–	–
Signing informed consent form		+	–	–	–	–	–
Demographics		+	–	–	–	–	–
Anamnesis		+	–	–	–	–	–
Previous treatment		+	–	–	–	–	–
PESI risk stratification		+	–	–	–	–	–
CTPA		+	+	–	–	–	–
EchoCG with PASP definition		+	+	–	+	+	–
Ultrasound diagnostics of the inferior vena cava		+	+	–	+	–	–
Assessment of vital signs		+	+	+	+	+	+
Determining the presence of hemodynamic collapse		+	+	+	+	–	–
Physical examination		+	–	–	–	–	–
Accompanying illnesses		+	–	–	–	–	+
Changes in organs and systems		–	+	+	+	+	–
ECG		+	+	–	+	+	–
Coagulogram		+	+	–	–	–	–
General blood test		+	+	–	+	+	–
Biochemical blood test		+	–	–	–	+	–
General urine test		+	+	–	–	+	–
Fortelyzin® or Actilyse® administration		+	–	–	–	–	–
Concomitant therapy changes		–	+	+	+	+	+
Registration of AE and SAE		–	+	+	+	+	+
Assessment of bleedings		–	+	+	+	+	–

9. TRIAL PROCEDURES

Visit 1 (Start of the trial)

Prior to administration of the trial drug, all patients will undergo the following procedures:

- determination of inclusion/non-inclusion criteria
- signing of informed consent form
- collection of demographic data (date of birth, sex, body weight)
- collection of medical history (duration of the underlying disease, previous therapy, allergological anamnesis, etc.)
- physical examination
- evaluation of changes by organs and systems
- PESI mortality stratification
- CTPA
- EchoCG
- ultrasound diagnostics of the inferior vena cava
- determining the presence of hemodynamic collapse
- ECG
- blood sampling for hematological and biochemical analyses
- coagulogram
- general urine analysis
- randomization
- Fortelyzin® or Actilyse® administration

Assignment of individual patient identification code (IPIC)

The Investigator must ensure the anonymity of the trial subjects. The full names of all patients participated in the trial are strictly confidential.

After signing the Informed Consent Form, each patient will be assigned an Individual Patient Identification Code (IPIC) in accordance with the current legislation (Table 6).

Table 6. Individual Patient Identification Code

Permission of the Ministry of Health of the Russian Federation No.	Permission's date of issue, DD/MM/YYYY/	Serial number of the medical organization specified in the Permission	Patient's initials	Patient's date of birth, DD/MM/YYYY/	A unique number assigned to the patient by the Investigator, consisting of letters and numbers (the name of the protocol and the screening number under which the patient was included in the trial)
--	---	---	--------------------	--------------------------------------	--

IPIC is established by the Insurant based on the patient data provided by the Investigator. The individual patient identification code is reported by the Insurant to the Investigator for inclusion in his medical documentation. The IPIC will be reflected in the primary documentation, CRF, and in the informed consent form. The IPIC will be transmitted by the Code Registry by the Insurant to the Insurer.

IPIC assigned to the patient is not subject to change.

The Investigator should maintain a separate Identification Registry containing the individual numbers, surnames, dates of birth, addresses, phone numbers, and medical records (if available). Only the initials, dates of birth, and unique patient numbers that are IPIC part will be used in the report and trial documentation.

The randomization plan will be known by the Principal Investigator and Regulatory Authorities.

Visit 2. (The first day after thrombolysis)

- assessment of vital signs – every hour
- determining the presence of hemodynamic collapse
- changes in organs and systems
- CTPA
- EchoCG
- ultrasound diagnostics of the inferior vena cava
- ECG
- blood sampling for hematological analyse
- coagulogram
- general urine analysis
- registration of AE and SAE
- assessment of bleedings
- concomitant therapy changes

Visit 3. (The second day after thrombolysis)

- Assessment of vital signs (twice per day)
- determining the presence of hemodynamic collapse
- changes in organs and systems
- registration of AE and SAE
- assessment of bleedings
- concomitant therapy changes

Visit 4. (The 7th day after thrombolysis)

- assessment of vital signs (twice per day)
- determining the presence of hemodynamic collapse
- changes in organs and systems
- EchoCG
- ultrasound diagnostics of the inferior vena cava
- ECG

- blood sampling for hematological analyse
- registration of AE and SAE
- assessment of bleedings
- concomitant therapy changes

Visit 5. (Discharge)

- assessment of vital signs
- changes in organs and systems
- EchoCG
- ECG
- blood sampling for hematological and biochemical analyses
- general urine analysis
- registration of AE and SAE
- assessment of bleedings
- concomitant therapy changes

Visit 6. (Day 30 after thrombolysis)

- assessment of vital signs
- registration of AE and SAE
- assessment of bleedings
- concomitant therapy changes

Unscheduled visits

Unscheduled visits may be made at the discretion of the Investigator or at the initiative of the patient. For all unscheduled visits, the corresponding CRF page should be filled out.

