Efficacy criteria:	
 • Primary efficacy outcome – death from any causes within 7 days • Secondary efficacy outcome – PASP (V₁, V₂, V₄, V₅) • Secondary efficacy outcome – hemodynamic collapse within 7 days • Secondary efficacy outcome – recurrent PE within 7 days • Secondary efficacy outcome – death from PE within 7 days • Secondary efficacy outcome – death from any causes within 30 days • Secondary efficacy outcome – clinical composite of hemodynamic collapse within 7 days + recurrent PE within 7 days + death from any causes within 30 days
Safety criteria:	
 • Safety outcomes – ischemic and hemorrhagic strokes within 7 days • Safety outcomes – bleedings BARC type 3 and 5 • number and severity of SAEs and AEs in organs and systems

Conclusion:	Each research center prepares a report, which is signed by the Principal Investigator and approved by the head of the medical institution, where the center is based. The submission deadline is up to 1 month after the completion of the trial. The statistical processing is carried out by an independent statistical expert according to the case report form.
--------------------	---

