4.2. Informed consent form

Informed consent will be obtained from all prospective study participants before any research procedures are initiated. Prior to this, the Investigator must fully inform a patient about all aspects of clinical research, including its purposes, study procedures, expected risks and benefits of participation, and voluntariness of participation.

The patient must be provided with written information about the study (Informed consent form), approved by the Ethics Committee. The patient's informed consent form contains all information about the planned clinical trial, as well as the terms of

confidentiality and the use of the patient's data. The rights, safety, and well-being of the participants will take priority and prevail over the science and society interests. If necessary, information about the procedure for obtaining informed consent from patients/volunteers can be submitted to the Ethics Committee.

Prior to the patient's participation in the clinical trial, two copies of the Informed consent form with the patient's name must be signed and personally dated by the patient or the patient's legal representative, or by a person who conducted the informed consent discussion. One copy of signed and dated written Informed consent form will be provided to the patient, and the other will be kept by the Investigator.

When the patient's condition does not allow him/her to express his/her will and there is no legal representative and the need for treatment is urgent, the question of medical intervention in the interest of the patient and his/her inclusion in the study is resolved by a council of physicians, and if it is not possible – by his/her attending (duty) physician with following notification of the Principal Investigator, officials of the clinical site and the legal representative.

The Informed consent form must be reviewed and approved by the Ethics Committee. The final version of the Study Protocol and Informed consent form must be approved by the Russian Ministry of Health and the Local Ethics Committee (if any) at the clinical site.

All subsequent amendments to the above-mentioned documents will also be submitted for approval to these institutions. In addition, these same institutions will be informed about all adverse events associated or possibly related to the use of the study drug.

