7.2. Exclusion criteria

- Increased risk of bleeding:
 - extensive bleeding at present or within the previous 6 months, hemorrhagic diathesis;
 - intracranial (including subarachnoid) hemorrhage at present or in history, suspicion of a hemorrhagic stroke;
 - hemorrhagic stroke or unknown etiology stroke in anamnesis;
 - ischemic stroke or transient ischemic attack within the last 6 months, with the exception of the current acute ischemic stroke within 4.5 hours;
 - central nervous system diseases in anamnesis (including neoplasms, aneurysm, surgery on the brain or spinal cord);
 - major surgery or major trauma within the previous 3 months, recent traumatic brain injury;
 - prolonged or traumatic cardiopulmonary resuscitation (> 2 min), labor within the previous 10 days, recent puncture of an uncompressible blood vessel (eg, subclavian or jugular vein);
 - severe liver disease, including liver failure, cirrhosis, portal hypertension (including esophageal varices) and active hepatitis;

- confirmed peptic ulcer of the stomach or duodenum within the last three months;
- a neoplasm with an increased risk of bleeding;
- simultaneous treatment with oral anticoagulants, for example, warfarin with INR>1.3;
- arterial aneurysms, defects in the development of arteries / veins;
- severe uncontrolled arterial hypertension;
- acute pancreatitis;
- bacterial endocarditis, pericarditis;
- suspicion of a dissecting aortic aneurysm;
- any other conditions, in the opinion of the doctor, associated with a high risk of bleeding.

- Lactation, pregnancy
- Known hypersensitivity to Actilyse®, Fortelyzin®.

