20. REPORTING

Each clinical site compiles a report, which is signed by the Principal Investigator and approved by the head of the medical institution on the basis of which the center is located.

The statistical processing is carried out by an independent statistical expert on the basis of the CRF.

The deadline for report submission is up to one month after the completion of the trial.

The final report will contain clinical and statistical reports, as well as appendixes with individual data and statistical analysis.

The suggested structure of the report: the purpose of the trial, methods (including any deviations from the Trial Protocol), evaluation of the results, discussion of adverse events, and their interpretation.

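### Section 9 gives the Principal Investigator, who appears to be a site-level role, the randomization plan without limit; if that means the allocation sequence, concealment can fail in this open-label, envelope-randomized trial

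*Combined protocol and SAP*

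**What the plan says.** Section 9 (Trial procedures), in the text on patient identification codes under Visit 1, contains one sentence on access to the randomization: "The randomization plan will be known by the Principal Investigator and Regulatory Authorities". It does not say from when, until when, or what the plan contains.

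Other places bear on how to read it:

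- **The role.** The term is not defined. The Protocol summary (Conclusion) says "Each research center prepares a report, which is signed by the Principal Investigator and approved by the head of the medical institution", and section 20 says "Each clinical site compiles a report, which is signed by the Principal Investigator". Section 4.2 names the role alongside officials of the clinical site.
- **The design.** The Protocol summary describes "A multicenter, open-label, randomized, comparative, parallel-group non-inferiority trial of efficacy and safety".
- **The method.** Section 8: "patients will be randomized using the «envelope method» into two equal groups of 155 patients each". The Protocol summary places this in the clinical centers and also gives the 1:1 scheme.
- **Patient order.** In each center a patient is "assigned a serial number that corresponds to the sequence of patient inclusion in the trial" (section 8).
- **Discretion at entry.** Section 7.2 excludes patients with "any other conditions, in the opinion of the doctor, associated with a high risk of bleeding".
- **Emergency route.** Where the patient cannot express their will, no legal representative is available and treatment is urgent, "inclusion in the study is resolved by a council of physicians", or failing that by the attending or duty physician, and the Principal Investigator is notified afterwards (section 4.2).

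**The concern.** Randomization protects the comparison only if those deciding whether a patient enters cannot know which drug comes next. Section 9 appears to give that knowledge to a role found at every site. Listing randomization after eligibility, consent and baseline tests, as section 9 does for Visit 1, guards against staff who cannot foresee the assignment. It does not guard against someone who already holds the list.

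The primary endpoint, all-cause death within 7 days, is objective, so biased outcome assessment is a small worry. Selection at entry works earlier: it changes the risk mix of the arms before any outcome is recorded, and analysis afterwards cannot reliably undo it. The direction is open. Lower-risk patients steered to Fortelyzin would push towards a false non-inferiority finding. Higher-risk patients steered to it would push towards missing true non-inferiority.

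**Working it through.** **Step 1: what the sentence most naturally means.**

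- *Who.* A report per site, each signed by the Principal Investigator (Protocol summary; section 20), together with the pairing with site officials (section 4.2), points to a site-level role. No available text describes a trial-level one.
- *What.* The general scheme (envelopes, 1:1, 155 per arm) is printed in the Protocol summary and section 8, and section 4 requires all parties to sign the protocol. Naming two parties who will know the plan adds little unless it holds something that is not already printed. This is inference, not proof.
- *Enrolment.* No section keeps Principal Investigators out of screening or enrolment, and none assigns them that task.
- *Order.* Patients are numbered in order of inclusion. That envelopes are used in a fixed order is an assumption; the documents do not tie the two together.

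**Step 2: reproduce the plan's sample size.** Section 17 gives 10% mortality in both arms, a 10-point margin, one-sided 2.5% and 80% power. Its formula gives

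n = (1.960 + 0.842)² × (0.10×0.90 + 0.10×0.90) / 0.10² = 141.3 per arm,

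which agrees with the stated 141. Also 141 × 1.10 = 155.1, which agrees with 155.

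**Step 3: sensitivity to an assumed shift.** The documents give no size for this bias. Let a shift s be applied to observed Fortelyzin mortality p₁, with Actilyse mortality p₂ = 10% and n = 141. With a Wald limit and normal approximation, the probability of declaring non-inferiority is

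Φ( (0.10 − (p₁ − p₂)) / SE − 1.96 ), SE = √[ (p₁(1−p₁) + p₂(1−p₂)) / 141 ].

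- *Type I error:* the truth is 20% vs 10% (at the margin), and p₁ is observed as 20% − s.
- *Power:* the truth is 10% vs 10%, and p₁ is observed as 10% + s.

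| s (points) | p₁, type I | SE | Type I error | p₁, power | SE | Power |
|---|---|---|---|---|---|---|
| 0 | 20.0% | 0.0421 | 2.5% | 10.0% | 0.0357 | 79.9% |
| 0.5 | 19.5% | 0.0419 | 3.3% | 10.5% | 0.0361 | 74.9% |
| 1 | 19.0% | 0.0416 | 4.3% | 11.0% | 0.0365 | 69.3% |

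Example, s = 1 point: type I error = Φ(0.01/0.0416 − 1.96) = Φ(−1.72) = 4.3%.

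Section 18 names neither a Wald limit nor a score test for the non-inferiority comparison. Exact enumeration of the Farrington–Manning score test gives type I error of 2.4%, 3.2% and 4.1%, and power of 78%, 72% and 67%. The pattern is the same.

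**Step 4: how much selection a shift needs.** Assume risk strata of 25% and 5%. A 10% average implies 25% high-risk patients (0.25×25% + 0.75×5% = 10%), about 35 in an arm of 141. Each high-risk patient replacing a low-risk one moves the arm by 0.20/141 = 0.14 points. So 0.5 points needs 0.005 × 141/0.20 ≈ 4 patients, 1 point about 7, and 2 points about 14. The last is 14/35 = 40% of one arm's high-risk count, always in the same direction. These strata fit the 10% power case only. They do not average to the 20% used for type I error, so the patient counts do not carry over to that column.

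**The case against.** The strongest reply is that the sentence is a safeguard. Naming only two parties may be meant to keep the plan from everyone else, and it follows directly on text about confidentiality and the restricted identification registry. 'Plan' may also mean only the scheme, which reveals no upcoming assignment. Enrolment-related tasks are given to the Investigator or to other physicians: informing the patient and keeping the consent form (section 4.2), and the physical examination (section 9.1.3). In the emergency route the Principal Investigator hears afterwards. The serial number is a case report form identifier that nothing links to the envelopes.

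Much of this stands. The access-limit reading is fair, and nothing says that other enrolling staff see the plan. But on that reading the Principal Investigator still has it, and no text bars that person from enrolling. The emergency route is confined to the circumstances listed in section 4.2. The scheme-only reading is possible but weaker, for the reason given in Step 1.

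The size is also open to challenge. Every shift is assumed. If the role is site-level, each Principal Investigator acts at one site, so a large trial-wide shift would need the same behaviour in the same direction at several sites. A reader might take a 2-point shift as a realistic case (type I error about 7.0%, power about 57%). The amount of one-way selection in Step 4 argues against relying on it.

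**Conclusion.** The point holds as a conditional design risk. As written, the sentence gives an apparently site-level role unlimited knowledge of what is most naturally the allocation sequence. Followed literally, that can defeat concealment in an open-label trial with a discretionary exclusion. The risk needs three things together: the plan is the sequence, envelopes follow a fixed order, and the holder takes part in enrolment. The documents confirm none of the three and exclude none.

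A reader might infer that concealment is broken, or that the bias would favour Fortelyzin. The documents support neither: they show no misuse, and selection could run either way. The 0.5 to 1 point results in Step 3 show sensitivity to an assumed shift and do not estimate an expected bias.

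The envelope procedure (sealing, numbering, custody, opening) is not described in the available text. That alone would be missing detail. The point rests on the affirmative access statement in section 9. It should be fixed because the correction is nearly free and selection bias cannot be repaired after enrolment. Confidence is medium, because both key terms are undefined.

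**What to change.** Amend the section 9 sentence so that no one involved in screening or enrolment, including site Principal Investigators, has access to the allocation sequence until enrolment ends. Have the list held by a party independent of the sites, for example the independent statistical expert already named in section 20. If only the general scheme was meant, say so in the same sentence and define the Principal Investigator role.

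The cost is one amended sentence and a small list-holding duty; section 20 currently gives the statistical expert only the statistical processing. Sample size, endpoints and treatment do not change.
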